3.3 Inclusion of Women and Minorities

Both men and women and members of all races and ethnic groups are eligible for this trial.

4. TREATMENT PLAN

4.1 Suberoylanilide Hydroxamic Acid (VORINOSTAT) Administration

Treatment will be administered on an outpatient basis. Reported adverse events and potential risks are described in Section 6. Appropriate dose modifications for VORINOSTAT are described in Section 5. No investigational or commercial agents or therapies other than those described below may be administered with the intent to treat the patient's malignancy.

A cycle of therapy will consist of VORINOSTAT 200mg twice daily administered orally for 14 days followed by a seven day break on a 21 day cycle for the first cycle. If tolerated, the dose may be increased after the 2nd cycle to 200 mg TID x 14/21 days. If necessary, dose de-escalation may be instituted by reducing one of the daily doses by 100 mg; so, for example, patients might receive an am dose of 300 mg and a pm dose of 200 mg. Rituximab will be infused on day 1 of each cycle at the standard dose of 375 mg/m². Radiological assessment by CT and/or PET scan will take place at baseline and after every three cycles (every 3 months). Response will be assessed by standard criteria (Cheson BD, *et al* 1999). Toxicity will be assessed on days 1 and 8 of every cycle, and graded using the NCI CTCAE version 3.0. Patients with measurable response or stable disease may continue receiving VORINOSTAT until progression. Patients who achieve CR will receive two further cycles of VORINOSTAT plus rituximab and then discontinue drug. Patients who achieve complete response may be restarted on drug in the event of relapse six months or greater from the time of initial CR, given the chronic relapsing nature of indolent lymphomas. Compliance with treatment will be monitored by use of drug diaries.

Because many drugs including antineoplastic agents are metabolized by the cytochrome P450 system, there is a potential for interaction of VORINOSTAT with concomitantly administered drugs. The case report form must capture the concurrent use of all other drugs, over-the-counter medications, or alternative therapies.

Patient compliance will be monitored using drug diaries, which will be reviewed on day 1 of each cycle after cycle 1.

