As of June 2004, VORINOSTAT capsules have been administered to 143 patients with advanced solid tumors or hematologic malignancies in three phase 1 trials and three phase 2 trials (Investigator's Brochure, 2004) at total daily doses ranging from 200 to 900 mg. The MTD of continuous dosing (no rest period) of oral VORINOSTAT is 400 mg q.d. or 200 mg b.i.d. When the agent is given intermittently, the MTD is 300 mg b.i.d. daily × 3 days per week or 250 mg t.i.d. x 14 days followed by 7 days of rest. The DLTs are non-hematologic (anorexia, dehydration, diarrhea, and fatigue). The most common hematologic adverse events are anemia and thrombocytopenia, which are rapidly reversible after study drug interruption. Pharmacokinetic analysis of 26 patients has indicated that the bioavailability of oral VORINOSTAT is approximately 46%. VORINOSTAT doses in the range of 200 - 600 mg produced maximum concentration (C_{max}) and drug exposure (AUC) curves that were linearly proportional. The $t_{1/2}$ of oral VORINOSTAT ranges from 92 to 150 minutes, and preliminary data suggest that administration of VORINOSTAT with food does not appear to substantially alter the rate or extent of absorption. Inhibition of HDAC activity was achieved in PBMCs at the 200 mg dose level. At dose levels of 400 and 600 mg, the duration of HDAC inhibition lasted ≥ 10 hours.

Significant antitumor activity has been observed among members of the above patient population. In the ongoing phase 1 study of oral VORINOSTAT, seven patients with heavily pre-treated diffuse large B-cell lymphoma were entered. Among these patients, one complete response (CR) and one partial response (PR) were observed. In addition, one patient has had a significant PET scan response. The PR lasted 5 months, the PET scan response lasted 6 months, and the CR is ongoing with a duration >12 months. Decrease in tumor mass, pleural effusion, and improvement of tumor-related pain or shortness of breath have also been observed in patients with mesothelioma. In an ongoing phase 2 study of VORINOSTAT in patients with heavily pretreated CTCL or peripheral T-cell lymphoma, objective responses have been observed (including PRs in 5 of 13 patients), and 8 of

10 patients reported decreased pruritus. In the published Phase I study of VORINOSTAT, the MTD was identified as 200 mg PO bid for continuous dosing and 300 mg PO bid for three-day-per-week dosing (Kelly WK, et al 2005)

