5. DOSING DELAYS/DOSE MODIFICATIONS

5.1 Vorinostat Dose Reductions for Toxicity:

Treatment will be administered at 100 mg daily less than their previous dose for patients who present to treatment and are found to have $ANC \geq 500$, but ≤ 1000 , or platelet counts $\geq 50K$ but $\leq 75K$. This dose reduction is reversible with normalization of counts.

Treatment will be held for patients who present with:

1. non-hematologic toxicity of grade 3 or 4, until toxicity resolves to below grade 2. These patients will restart at 100 mg daily less than their previous dose. If this dose leads to recurrence of the toxicity at grade 3 or greater, the patient will come off study.
2. hematologic toxicity of ANC <500, or platelet count <50K. Should dose need to be held for greater than two weeks, upon recovery of ANC >1000 or platelet count >50 patient may restart at 100 mg daily less than their previous dose. If this dose also leads to ANC<500 or platelet count <50, then patient should come off study.

Treatment will be discontinued in patients who experience toxicity of grade 3 or greater that does not resolve within 3 weeks. Requirement for more than two dose reductions mandates removal from the study. Delay of protocol treatment for more than four weeks from date of scheduled treatment mandates removal from protocol treatment, unless there are extenuating circumstances and approved by the principal investigator.

Lovenox Dose Reductions for Toxicity:

Hematologic Toxicity: If platelet count drops to <50K, lovenox should be held until platelets recover.

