6. PHARMACEUTICAL INFORMATION

6.1 Suberoylanilide Hydroxamic Acid (NSC 701852)

Chemical Name: N-hydroxy-N'-phenyl-octane-1,8-dioic acid diamide;
N-hydroxyl-N'-phenyl (9CI) octanediamide

Other Names: VORINOSTAT, L-001079038, WIN 64652, MSK390, AP390

Classification: Antineoplastic

CAS Registry Number: 149647-78-9

Molecular Formula: C₁₄H₂₀N₂O₃ **M.W.:** 264

Approximate Solubility: Water ≤ 5 mg/mL

Description: Histone deacetylase (HDAC) inhibitor

Mode of Action: Histone deacetylases (HDACs) are a family of enzymes that regulate chromatin remodeling and gene transcription via the dynamic process of acetylation and deacetylation of core histones.

Suberoylanilide hydroxamic acid, a potent inhibitor of HDAC activity, binds directly to the catalytic pocket of HDAC enzymes. VORINOSTAT causes G1 or G2 phase cell-cycle arrest, apoptosis, or differentiation in cultured transformed cells.

How Supplied: Suberoylanilide hydroxamic acid is supplied by Merck and Co., Inc. Suberoylanilide hydroxamic acid is supplied in the following strengths:

1. a white, opaque gelatin capsule containing 100 mg (size 3 capsule) of suberoylanilide hydroxamic acid
2. a white, opaque gelatin capsule containing 200 mg (size 1 capsule) of suberoylanilide hydroxamic acid.

The inactive ingredients contained in each capsule are microcrystalline cellulose, sodium croscarmellose, and magnesium stearate.

Suberoylanilide hydroxamic acid 100 mg capsules are supplied in bottles of 120 capsules and 200 mg capsules are supplied in bottles of 100 capsules.

Storage: Store suberoylanilide hydroxamic acid capsules at room temperature, 15 to 30 °C (59 to 86 °F). Transient temperature spikes up to 40 °C (104 °F) for up to 24 hours are permissible.

Stability: Shelf life stability studies of the intact bottles are ongoing.

Route of Administration: Orally

Method of Administration: Unless otherwise stated in the protocol, suberoylanilide hydroxamic acid capsules must be administered whole. The absolute bioavailability of suberoylanilide hydroxamic acid under fasted or fed conditions is approximately 46%. Oral administration with food does not appear to substantially alter the rate or extent of absorption.

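### The de-escalation example in Section 4.1 (300 mg am + 200 mg pm) does not follow from its own rule under either permitted vorinostat schedule

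*Combined protocol and SAP*

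**What the plan says.** Section 4.1 of the protocol starts vorinostat at 200 mg twice daily for 14 days of each 21-day cycle; the Schema and footnote a of the Study Calendar agree. If this is tolerated, "the dose may be increased after the 2nd cycle to 200 mg TID x 14/21 days". These are the only two schedules the treatment plan allows before any reduction.

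Section 4.1 then deals with reductions: "dose de-escalation may be instituted by reducing one of the daily doses by 100 mg". The same sentence continues with an illustration: "so, for example, patients might receive an am dose of 300 mg and a pm dose of 200 mg".

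The section also points elsewhere for the detail: "Appropriate dose modifications for VORINOSTAT are described in Section 5". Section 5.1 works on the daily total: "Treatment will be administered at 100 mg daily less than their previous dose". It does not say how the reduced total is divided over the day, and it has no dose-level table. It takes a patient off study if more than two reductions are needed, or if the toxicity recurs at the reduced dose.

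**The concern.** The rule lowers one dose by 100 mg. Every single dose in the permitted schedules is 200 mg, so applying the rule cannot produce a 300 mg dose. The example therefore contradicts the instruction it is meant to illustrate.

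This is the protocol's only worked illustration of a reduced vorinostat dose, and sites will turn to it when a patient has toxicity. For an escalated patient, one site could follow the rule and another the example, and they would prescribe different schedules. Compliance is checked with drug diaries (Section 4.1), and Section 9.2 allows no treatment deviations except delays, so a site needs to know which split complies. Since recurrence at the reduced dose, or a third reduction, ends participation under Section 5.1, the reduced dose should be unambiguous. The worst case is a patient on the starting dose who is given the example's 500 mg/day as a supposed reduction.

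**Working it through.** **Inputs**

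- Starting schedule: 200 mg twice daily, 14 of 21 days (Section 4.1, Schema, Study Calendar footnote a).
- Escalated schedule: 200 mg three times daily, 14 of 21 days (Section 4.1).
- Rule: take 100 mg off one of the daily doses (Section 4.1), or 100 mg off the daily total (Section 5.1).
- Maximum number of reductions: two (Section 5.1).
- Example to reproduce: 300 mg am + 200 mg pm = 500 mg/day (Section 4.1).

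**Step 1: try to reproduce the example.** Take 100 mg off any one dose, once and then twice, from each permitted schedule.

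| Starting from | Daily total | After one reduction | After two reductions | 300+200 reached? |
|---|---|---|---|---|
| 200 mg twice daily | 2 × 200 = 400 mg | 200+100 = 300 mg | 100+100, or a single 200 = 200 mg | No |
| 200 mg three times daily | 3 × 200 = 600 mg | 200+200+100 = 500 mg | 200+200, or 200+100+100 = 400 mg | No |
| 300 mg twice daily (not permitted here) | 2 × 300 = 600 mg | 300+200 = 500 mg | 200+200, or 300+100 = 400 mg | Yes, after one |

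The example follows exactly from 300 mg twice daily. In the documents, oral vorinostat at that dose appears only in the background of Section 2.3.4, as "300 mg PO bid for three-day-per-week dosing", a schedule this trial does not use.

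**Step 2: the closest permitted reading.** The example's total, 300 + 200 = 500 mg, equals 600 − 100 mg, so it agrees with Section 5.1 for an escalated patient reduced once. To get from 200+200+200 to 300+200, one dose is dropped and another is raised by 100 mg.

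- Largest single dose: 300 against 200 mg, 300/200 = 1.5, or +50%.
- Doses per day: two instead of three.
- Cycle total: 14 × 500 = 7,000 mg under either split.

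**Step 3: misapplied to a starting-dose patient.**

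- Required by Section 5.1: 400 − 100 = 300 mg/day, 300/400 = 0.75, or −25%.
- Under the example: 500 mg/day, 500/400 = 1.25, or +25%.
- Per cycle: 14 × 500 = 7,000 mg against 14 × 300 = 4,200 mg, a difference of 2,800 mg.

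**Step 4: against the reported tolerance.** Section 2.3.4 gives an oral maximum tolerated dose of "250 mg t.i.d. x 14 days followed by 7 days of rest", that is 3 × 250 = 750 mg/day on the same 14-on, 7-off pattern. 500/750 = 67%. That figure does not cover the combination with rituximab.

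**The case against.** The strongest defence is that the governing rule is in Section 5.1 and is clear. It reduces the daily total and leaves the split open. The sentence in 4.1 is permissive and illustrative, and it comes directly after the sentence on escalation, so it is natural to read the example as an escalated patient cut to 500 mg/day and re-divided into morning and evening doses. On that reading the sum is right and only the re-division is unstated. Nor is a 300 mg single dose alarming in itself. Section 2.3.4 reports 400 mg once daily as a continuous-dosing maximum tolerated dose and a recommended phase 2 dose, with exposure proportional to dose from 200 to 600 mg. Giving a starting-dose patient more drug under the name of de-escalation would contradict both the rule beside it and Section 5.1. Even then, 500 mg/day is below the 600 mg/day the trial allows after escalation.

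Most of this stands as to size. The daily total is the same under either reading for an escalated patient, the misuse is unlikely, and nothing in the documents shows that it has happened. The tolerance data are, however, for vorinostat alone.

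It does not remove the contradiction. The text does not limit the example to escalated patients and does not say that three doses become two. Dropping one dose and raising another is not the operation the sentence describes. Section 5.1, the Schema and the calendar give no split that would settle the matter.

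**Conclusion.** The concern holds. The example in Section 4.1 cannot be derived from the rule in its own sentence under either permitted schedule, after one reduction or two. Its 500 mg/day total fits only a patient escalated to three-times-daily dosing and reduced once. For that patient the practical difference is in the schedule: two doses instead of three, and a largest dose of 300 instead of 200 mg, with the same daily and cycle totals. The figures of +25% against −25%, and 7,000 against 4,200 mg per cycle, apply only if the example is misapplied to a starting-dose patient. That risk is limited and should not set the weight of the point.

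This assumes that 200 mg twice daily and 200 mg three times daily are the only schedules from which a first reduction is made, as Section 4.1 states. It is an error in an operative dosing instruction and should be corrected. It has no bearing on the response endpoint, the sample size or the stopping rule.

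**What to change.** Delete the example in Section 4.1, or replace it with one for each schedule, with a reference to Section 5.1:

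- from 200 mg twice daily: 200 mg + 100 mg (300 mg/day);
- from 200 mg three times daily: 200 mg + 200 mg + 100 mg (500 mg/day).

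Both are deliverable, because Section 6.1 lists a capsule "containing 100 mg (size 3 capsule) of suberoylanilide hydroxamic acid" alongside the 200 mg strength.

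If the investigator does intend 300 mg + 200 mg for escalated patients, keep it, but state that it applies only after escalation to three-times-daily dosing and that the patient then takes two doses a day.

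The cost is one sentence in Section 4.1 and a notification to sites. The Schema, calendar, sample size and analysis need no change.

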4.2 Rituximab Administration

Rituximab will be administered at a dose of 375 mg/m² on day 1 of every cycle, every three weeks. The initial dose rate should be 50 mg/hour IV for the first hour. If no toxicity is seen, the dose rate may be escalated gradually to a maximum of 400 mg/hour. Subsequent doses have required much less infusion time. If the first dose of rituximab is well tolerated, the starting flow rate for subsequent doses is 100 mg/hour, then increased gradually (100 mg/hour increments at 30-minute intervals) not to exceed 400 mg/hour.

Patients may experience transient fever and rigors with infusion. When these occur, the antibody infusion should be temporarily discontinued or slowed. When symptoms improve, the infusion should be resumed, initially at half the previous rate. Following the antibody infusion, the intravenous line should be kept open for medications, as needed. If there are no complications, the intravenous line may be discontinued after one hour of observation.

Oral premedication (acetaminophen and diphenhydramine hydrochloride) may be administered 30 to 60 minutes prior to starting each infusion of rituximab.

Lovenox Administration

Lovenox (enoxaparin) will be administered at a dose of 40 mg subcutaneously daily. Patients will be educated by nursing staff on how to perform daily injections. Administration should be alternated between left and right anterolateral and left and right posterolateral abdominal wall. The whole length of the needle should be introduced into a skin fold held between the thumb and the forefinger. The skin fold should be held throughout the injection.

4.3 Supportive Care Guidelines

4.3.1 Antiemetics

Individualization of antiemetic treatment for patients receiving VORINOSTAT is required, as some patients require no antiemetic therapy, while others may require more intense therapy. Recommended antiemetics include: ondansetron, prochlorperazine, metoclopramide, lorazepam, or diphenhydramine. It is recommended that steroids not be used for anti-emesis.

4.3.2 Chemotherapy

Concurrent chemotherapy is not allowed in this study.

4.3.3 Complimentary or Alternative medications

Patients may not take CAM medications while on protocol. Routine vitamin supplementation is allowed.

4.3.4 Growth Factors

Patients already on erythropoietin or aranesp for lymphoma related anemia may continue to use these agents. Use of G-CSF or erythropoietin is allowed after the first cycle.

4.3.5 Radiation Therapy

Patients who require localized external beam radiotherapy at the time of protocol screening should receive it prior to study entry.

Patients who require localized external beam radiotherapy during study will be considered to have progression of lymphoma and will be removed from study.

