3. PATIENT SELECTION

3.1 Eligibility Criteria

- 3.1.1** Patients must have histologically or cytologically confirmed indolent Non-Hodgkin's Lymphoma (Included in this category are newly diagnosed or relapsed/refractory follicular center lymphomas grade I, II, III, relapsed /refractory marginal zone B-cell lymphoma (nodal and extranodal), relapsed/refractory mantle cell lymphoma).
- 3.1.2** Patients must have measurable disease by CT scan. PET scan evaluations are desirable but not mandatory, so that patients with negative PET scans but measurable disease by CT are eligible.
- 3.1.3** Patients may have had up to four prior chemotherapeutic regimens. Steroids alone and local radiation do not count as regimens (Radiotherapy must have been completed at least 14 days prior to starting vorinostat). Rituxan alone does not count as a regimen, however, Bexxar or Zevalin do. For treated patients, the most recent therapy must have failed to induce a complete response (i.e. there is persistent disease by CT or PET), or there must be disease progression or recurrence after the most recent therapy.
- 3.1.4** Patients may be enrolled who relapse after autologous stem cell transplant if they are at least three months after transplant, and after allogeneic transplant if they are at least six months posttransplant. To be eligible after either type of transplant, patients should have no active related infections (i.e. fungal or viral). In the case of allogeneic transplant relapse, there should be no active acute graft versus host disease (GvHD) of any grade, and no chronic Graft versus Host disease other than mild skin, oral, or ocular GvHD not requiring systemic immunosuppression.
- 3.1.5** Age ≥ 18 years. Because no dosing or adverse event data are currently available on the use of VORINOSTAT in patients < 18 years of age, children are excluded from this study but will be eligible for future pediatric single-agent trials, if applicable.
- 3.1.6** Life expectancy of greater than 3 months.
- 3.1.7** ECOG performance status 2 (Karnofsky $\geq 60\%$; see Appendix A).
- 3.1.8** Patients must have normal organ and marrow function as defined below:
- Absolute Neutrophil Count $\geq 1,000/\text{mcL}$
 - platelets $\geq 100,000/\text{mcL}$
 - total bilirubin within normal institutional limits; patients with elevation of unconjugated bilirubin alone, as in Gilbert's Disease, are eligible.

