3. The spleen and/or liver, if considered enlarged before therapy on the basis of a physical examination or CT scan, should not be palpable on physical examination and should be considered normal size by imaging studies, and nodules related to lymphoma should disappear. However, determination of splenic involvement is not always reliable because a spleen considered normal in size may still contain lymphoma, whereas an enlarged spleen may reflect variations in anatomy, blood volume, the use of hematopoietic growth factors, or causes other than lymphoma.

4. If the bone marrow was involved by lymphoma before treatment, the infiltrate must have cleared on repeat bone marrow biopsy. The biopsy sample on which this determination is made must be adequate (with a goal of > 20 mm unilateral core). If the sample is indeterminate by morphology, it should be negative by immunohistochemistry. A sample that is negative by immunohistochemistry but that demonstrates a small population of clonal lymphocytes by flow cytometry will be considered a CR until data become available demonstrating a clear difference in patient outcome.

Cru

The use of the above definition for CR and that below for PR eliminates the category of CRu.

PR

The designation of PR requires all of the following:

1. At least a 50% decrease in sum of the product of the diameters (SPD) of up to six of the largest dominant nodes or nodal masses. These nodes or masses should be selected according to all of the following: they should be clearly measurable in at least 2 perpendicular dimensions; if possible they should be from disparate regions of the body; and they should include mediastinal and retroperitoneal areas of disease whenever these sites are involved.
2. No increase should be observed in the size of other nodes, liver, or spleen.
3. Splenic and hepatic nodules must regress by $\geq 50\%$ in their SPD or, for single nodules, in the greatest transverse diameter.
4. With the exception of splenic and hepatic nodules, involvement of other organs is usually assessable and no measurable disease should be present.
5. Bone marrow assessment is irrelevant for determination of a PR if the sample was positive before treatment. However, if positive, the cell type should be specified (eg, large-cell lymphoma or small neoplastic B cells). Patients who achieve a CR by the above criteria, but who have persistent morphologic bone marrow involvement will be considered partial responders.

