10. STATISTICAL CONSIDERATIONS

10.1 Study Design/Endpoints

Response rate (CR+PR) will be the primary endpoint. An underlying 20% response rate will be regarded as not sufficiently active, and the trial is designed to have little chance of missing a 40% response rate. A two-stage design will be used. In the first stage, 17 patients will be enrolled. If 4 or more respond, accrual will continue to a total of 33 patients, with 10 or more responses regarded as evidence of sufficient activity to warrant further investigation. If the true response rate is 20%, the proposed design has a 90% chance of declaring vorinostat plus rituximab insufficiently active, and a 55% chance of stopping early. If the true response rate is 40%, there is a 89% chance of concluding VORINOSTAT is sufficiently active. All patients beginning VORINOSTAT therapy will be included in response rates calculations, which will include exact binomial confidence intervals.

All reportable adverse events will be monitored by the PI and CRA, and reported as described in section 10. Reportable and non-reportable adverse events are routinely tabulated for phase II consortium trials as the reports arrive. The time to progression and overall survival will be estimated using the product-limit method of Kaplan and Meier. Toxicity information recorded will include the type, severity, time of onset, time of resolution, and the probable association with the study regimen. Tables will be constructed to summarize the observed incidence by severity and type of toxicity. Baseline information (e.g. the extent of prior therapy, extent of disease) and demographic information will be presented, as well, to describe the patients treated in this Phase II study.

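### A mass irradiated as little as 14 days before treatment can serve as measurable disease and as a target lesion, so a radiotherapy effect after the baseline CT can enter the CR+PR count

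*Combined protocol and SAP*

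**What the plan says.** **Radiotherapy before entry.** Section 4.3.5 says that patients who need localized external beam radiotherapy at screening "should receive it prior to study entry". Section 3.1.3 sets the interval: "Radiotherapy must have been completed at least 14 days prior to starting vorinostat". Section 3.2.1 likewise excludes radiotherapy within 2 weeks.

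**Measurable disease.** Section 3.1.2: "Patients must have measurable disease by CT scan". It sets no condition about a radiation field. For treated patients, section 3.1.3 accepts disease that merely persists after the latest therapy; progression or recurrence is an alternative, not a requirement.

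**Response.** PR item 1 in section 8.1 is "At least a 50% decrease in sum of the product of the diameters (SPD) of up to six of the largest dominant nodes"; the item covers nodal masses too. The masses are to be measurable in two dimensions, from disparate regions if possible, and to include mediastinal and retroperitoneal disease where involved. Prior irradiation is not mentioned. Response is assessed every three cycles, about 9 weeks.

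**Decision.** Section 10.1: "Response rate (CR+PR) will be the primary endpoint". The trial has one arm. Accrual continues on 4 or more responses in 17, and 10 or more in 33 count as activity. Neither section 10.1 nor section 10.5.1 has a rule for recently irradiated patients.

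**The concern.** In a single-arm trial every response is credited to the study drugs, because no control group shares the non-drug changes. If a target mass was irradiated shortly before treatment, part of its change between baseline and the 9-week scan may be due to radiotherapy. PR items 2 and 6 forbid growth and new sites elsewhere, but they do not require shrinkage elsewhere. A patient with stable unirradiated nodes and a resolving irradiated mass could therefore be scored PR.

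This is a question of lesion selection, separate from scan timing. The study calendar lets the baseline CT be up to 4 weeks old, so it could even precede radiotherapy. But a CT taken after radiotherapy removes only the shrinkage that came before that scan; later shrinkage still counts.

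The provisions on radiotherapy during the study (second paragraph of 4.3.5) and on planned concurrent radiation (3.2.5) do not cover radiotherapy finished before entry. Nor can the analysis repair this afterwards: section 10.5.1 keeps all eligible patients in the main analysis (allowing only for those never treated) and does not let subset analyses carry the efficacy conclusion.

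**Working it through.** **1. Reproduce the plan's design figures.** Inputs from section 10.1: null rate 20%, target rate 40%, continue on ≥4/17, success on ≥10/33.

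- P(early stop) = P(X₁ ≤ 3 | 17, p)
- P(declare active) = Σ over x₁ ≥ 4 of P(X₁ = x₁ | 17, p) × P(X₂ ≥ 10 − x₁ | 16, p)

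| True rate | Result | Computed | Stated |
|---|---|---|---|
| 20% | early stop | 0.549 | 55% |
| 20% | declared inactive | 0.901 | 90% |
| 40% | declared active | 0.888 | 89% |

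The plan's figures are right. The baseline chance of declaring a 20% regimen active is 1 − 0.901 = 0.099.

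**2. When could an irradiated mass alone meet PR item 1?** Let w be its share of the baseline SPD and s its later proportional shrinkage from radiotherapy. With no change elsewhere, item 1 needs w × s ≥ 0.5.

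- Full resolution (s = 1): w ≥ 0.50.
- 70% shrinkage (s = 0.7, assumed): w ≥ 0.5/0.7 = 0.71.

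Otherwise the remaining target masses must shrink by (0.5 − w·s)/(1 − w). For w = 0.5 and s = 0.7 that is (0.5 − 0.35)/0.5 = 30%, against 50% if all masses shrank alike.

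**3. The opposite case.** If the irradiated mass is an inert residual (s = 0) and w = 0.5, the other masses must shrink by 0.5/0.5 = 100% to reach item 1. Where CR is judged on CT alone (CR item 2b), a residual that stays above normal size also blocks CR.

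**4. Effect on the decision, by assumption.** Suppose a fraction f of patients have such a mass, and a fraction c of the true non-responders among them are scored as responders. Neither figure is in the documents. At a true rate of 20%:

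apparent rate = 0.20 + 0.80 × f × c

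| f | c | Apparent rate | Expected extra responders in 33 | P(early stop) | P(declare active) |
|---|---|---|---|---|---|
| 0 | – | 20% | 0 | 0.549 | 0.099 |
| 5% | 10% | 20.4% | 33 × 0.004 = 0.13 | 0.532 | 0.110 |
| 5% | 50% | 22% | 33 × 0.02 = 0.66 | 0.467 | 0.160 |
| 10% | 50% | 24% | 33 × 0.04 = 1.32 | 0.389 | 0.237 |

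The table covers upward misclassification only; step 3 would pull the other way.

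**The case against.** The case against has real force on four counts.

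- **Direction.** A reader might infer that the bias can only favour declaring activity. The documents do not support that. Step 3 shows that an inert residual makes PR harder and can block CR.
- **PR needs more than item 1.** The other conditions must also hold: no growth of other nodes, liver or spleen; splenic and hepatic nodules down by at least 50%; no measurable disease in other organs; no new sites. Using up to six masses, from disparate regions if possible, dilutes a single local field. These conditions limit how often a false PR can arise, but they do not exclude one.
- **Unsupported inputs.** Conversion of one half has no source in the documents, and full resolution of a mass that still makes up half the SPD after radiotherapy is a generous assumption. With 10% conversion the effect is about one percentage point (9.9% to 11%).
- **Reading too much into the text.** A reader might take section 4.3.5 to send patients to radiotherapy immediately before entry, or assume that the irradiated mass will usually be among the six largest. The section says only that it precedes entry, 14 days is a minimum, and nothing says which masses are irradiated or why. Nor do the documents say how long radiotherapy shrinkage continues.

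Section 8.1 also adopts published criteria, so the remedy is an addition to them. That does not close the gap: sections 3.1.2 and 8.1 still allow an irradiated mass to be the only measurable disease and a target lesion.

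**Conclusion.** The point holds as a gap in the response rules. As written, a patient irradiated 14 days before vorinostat can enter on the irradiated mass, have it measured as a target, and have its later change credited to the study drugs. Attribution is compromised in both directions. The more consequential error is a false PR, which needs an irradiated mass of at least half the SPD if it resolves fully, or about 71% if it shrinks by 70%, with every other PR condition met.

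The size cannot be estimated from the documents. The 11%, 16% and 24% are sensitivity values that rest on assumed f and c, and should not be read as this trial's false-positive rate. If no patient was recently irradiated, the rate stays at 9.9%. The design calculation itself is sound. The change is worth making because the thresholds of 4/17 and 10/33 are low counts, at which one misattributed response can turn a decision, and because the remedy is short.

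**What to change.** **Section 8.1:** state that a mass irradiated shortly before entry, within a window that the sponsor specifies, is not a target lesion for the SPD unless existing imaging shows that it has grown since radiotherapy.

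**Section 3.1.2:** require at least one measurable lesion that either lies outside the recent field or has grown since radiotherapy. The either/or matters, because it keeps patients whose only disease is documented in-field progression. The window keeps the rule from reaching back to radiotherapy given years earlier.

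**Cost:** about one sentence in each section. A few patients whose only measurable disease was recently irradiated and has not grown become ineligible. No scans are added, because a mass without a comparison scan is simply not used as a target. Sample size, decision thresholds and treatment are unchanged.
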